On Day 5, subjects randomized to 200 mg CAMB and 400 mg CAMB will be administered a single dose of 200 mg and 400 mg, respectively, in the clinic with a non-standardized meal or snack.

Other combinations of CAMB dosing are allowed throughout the study such that subjects randomized to 200 mg CAMB complete a course of ten 100 mg doses by Day 5 and subjects randomized to 400 mg CAMB complete ten 200 mg doses by Day 5. Subjects will be instructed to record their dosing in a patient diary.

Subjects randomized to fluconazole will take a single 150 mg tablet on Day 1 without respect to food.

Visit Schedule

Participation in this study will consist of a screening period (up to 48 hours prior to Day 1); a 5-day treatment period (5 days with 200 mg or 400 mg CAMB or 1 day with fluconazole); a mandatory pre-dose PK assessment on Day 5 for determination of trough plasma concentrations of CAMB; an optional serial PK assessment for subjects who agree to participate; a TOC/Early Withdrawal Visit on Day 12 (± 2 days), and a follow-up phone call between Days 21 to 30. For eligible subjects, screening and Day 1 can occur on the same day. Therefore, subjects who do not participate in the optional serial PK assessment will complete a total of 3 to 4 clinic visits, and subjects who do participate will complete a total of 4 to 5 clinic visits.

At screening, subjects must provide written informed consent prior to any study procedures being performed. Papanicolaou (Pap) smear/tests will be performed for subjects (>21 years of age) who do not have a negative test for intraepithelial lesion or malignancy or atypical squamous cells of

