On Days 5 and 12, subjects will undergo a speculum examination of the vagina. Vaginal cultures will be sent to the central laboratory. *Candida* infections will be identified from vaginal cultures revealing filamentous hyphae/pseudohyphae and/or budding yeast cells identifying a *Candida* infection. Speciation and susceptibility testing will be repeated on all positive fungal cultures. Signs and symptoms of infection will also be assessed, including erythema, edema, excoriation, itching, burning, or irritation of the vagina and/or the vulva.

On Day 5 (± 1 day for subjects not participating in the optional serial PK assessment), mandatory pre-dose PK blood samples will be collected from all subjects for determination of trough plasma concentrations of CAMB.

The optional serial PK assessment will include approximately 24 subjects randomized to 200 mg or 400 mg CAMB, with approximately 12 subjects in each group. For subjects who consent to participate in the optional serial PK assessment, additional blood samples will be collected on Day 5 at 1, 2, 3, 4, 8, and 12 hours, and 24 hours post-dose. In circumstances where the 12-hour PK assessment is not feasible, it will not be required. On Day 5, subjects randomized to 200 mg CAMB and 400 mg CAMB will be administered a single dose of 200 mg and 400 mg, respectively, in the clinic with a non-standardized meal or snack regardless of participation in the optional serial PK assessment.

A follow-up phone call will occur between Days 21 to 30. Adverse events will be assessed.

Inclusion Criteria

A subject will be eligible for participation in the study if all of the following criteria are met:

1. Must provide written informed consent and authorize disclosure of protected health information before any study-specific evaluation is performed;
2. Is female age 18 to 65 years, inclusive;
3. Has documented or suspected clinical diagnosis of moderate to severe VVC, defined as having a positive 10% KOH or saline preparation from the inflamed vaginal mucosa or secretions revealing yeast forms (hyphae or pseudohyphae) or budding yeasts;
4. Has 2 or more of the following signs and symptoms characterized as moderate in severity: itching, burning, irritation, erythema, edema, and/or excoriation of the vagina/vulva;

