5. For women >21 years of age, documented Pap smear/test at baseline or during the previous 36 months reported as either “negative for intraepithelial lesion or malignancy” or “atypical squamous cells of undetermined significance;” Verbal documentation of the Pap smear results will be acceptable for this study; in circumstances where the results of the Pap smear are pending at the time of randomization, eligible subjects may be randomized;
6. Women of childbearing potential must have negative pregnancy test before randomization and may not be lactating or planning to become pregnant during the study period. A woman is considered of childbearing potential if she is not surgically sterile or if her last menstrual period was <12 months prior to screening;
7. Agreement of female subject of childbearing potential to use highly effective methods of contraception or to abstain from sexual intercourse. Acceptable methods of contraception for this study include use of intrauterine device or abstinence; all oral, transdermal, and hormonal contraceptives or selective estrogen receptor modulator contraceptives are acceptable as long as the dose and type have been stable for 3 months prior to screening;
8. Willing to refrain from the use of intravaginal products during the treatment period (eg, douches, spermicides, condoms, tampons, and diaphragms); and
9. Has vaginal pH ≤4.5 at screening.

Exclusion Criteria

A subject will be excluded from participation in the study if any of the following criteria are met:

1. Has an intolerance or hypersensitivity to any amphotericin B (AMB) product, any component of CAMB (eg, phosphatidylserine), or to azole antifungal drugs (eg, fluconazole, itraconazole, voriconazole, isavuconazole, and posaconazole);
2. Is currently receiving antifungal therapy unrelated to VVC or has evidence of systemic fungal infections requiring antifungal therapy;
3. Has received treatment for VVC within the past 30 days or has experienced 4 or more episodes of VVC diagnosed by a physician after clinical evaluation in the past 12 months, of which 2 of the 4 episodes were confirmed by positive *Candida* culture; subjects who only have self-reported episodes of VVC in the past may still be considered for participation;

4. Has another cause or suspected cause of vulvovaginitis (eg, *T. vaginalis*, bacterial vaginosis, genital herpes);
5. Has an active human papillomavirus infection;

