6. Has other urogenital infection(s) that would potentially alter their response to disease;
7. Has confirmed or suspected *N. gonorrhoea* or *C. trachomatis*;
8. Has another vaginal or vulvar condition that would confound the interpretation of clinical response;
9. Has a physiological or pathological condition that would confound the interpretation of clinical response (eg, cervicitis, aerobic vaginitis, atrophic vaginitis, and mucoid ectopy);
10. Has any of the following laboratory abnormalities at screening:
 - a. Alanine aminotransferase (ALT), or aspartate aminotransferase, or alkaline phosphatase levels $>5 \times$ upper limit of normal (ULN);
 - b. Total bilirubin level $>2.5 \times$ ULN;
 - c. Estimated creatinine clearance <70 mL/min;
 - d. Absolute neutrophil count less than 500 cells/ μ L; or
 - e. Potassium level ≤ 3.5 mmol/L;
11. Plans to undergo treatment or surgery for cervical intraepithelial neoplasia or cervical carcinoma during the study period;
12. Has any known azole-resistant *Candida* infection;
13. Has documented Type I diabetes mellitus, use of insulin, or glycosylated hemoglobin A_{1c} level $>10\%$ within 6 months of enrollment;
14. Has previously diagnosed human immunodeficiency virus seropositivity or clinically diagnosed acquired immunodeficiency syndrome or its related complex;
15. Has a known immunosuppressive condition (eg, end-stage renal disease) or is currently taking immunosuppressants, (eg, steroids, cyclosporine);
16. Is currently receiving therapy with a drug known to prolong QTc interval that is metabolized via the cytochrome P450 3A4 enzyme, such as cisapride, astemizole, pimozide, and quinidine;
17. Has been exposed to any investigational agent during the last month (30 days or 5 half-lives, whichever is longer) prior to screening; or
18. Has any other condition the Investigator believes would interfere with the subject's ability to provide informed consent, comply with study instructions, or puts the subject at undue risk.

DOSAGE FORMS AND ROUTE OF ADMINISTRATION:

Encocleated amphotericin B will be administered as a 5 mg/mL oral suspension of 200 mg (100 mg [20 mL] BID) or 400 mg (200 mg [40 mL] BID) amphotericin B on Days 1 through 5.

Fluconazole will be administered once as a single 150 mg tablet on Day 1.

ANALYSIS POPULATIONS:

The Intent-to-Treat Population (ITT) will include all subjects who were randomized.

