The Modified Intent-to-Treat (mITT) Population will include all randomized subjects who have a *Candida* species isolated on culture of vaginal specimen at baseline based on the central laboratory results.

The Safety Population will include all ITT subjects who received at least 1 dose of study drug.

The PK Population will include the subjects in the ITT Population with at least 1 PK sample.

The Per-Protocol Population will include all of the mITT subjects who meet the following criteria:

- No key inclusion/exclusion violations;
- Received the complete course of study drug;
- No major protocol violations that would affect the treatment evaluation; and
- Has not received another systemic or topical antifungal drug that has documented activity against the causative organism before the TOC assessment, unless the subject has a therapeutic response of failure at a previous assessment visit.

EFFICACY VARIABLES:

The efficacy endpoints for this study will be performed on the mITT Population and Per-Protocol Population and will include the following:

1. The proportion of subjects with clinical cure at the TOC Visit (Day 12);
2. The proportion of subjects with mycological eradication at the TOC Visit (Day 12); and
3. The proportion of subjects with overall success at the TOC Visit (Day 12).

For the definition of clinical cure, mycological eradication, and overall success, see below.

Assessment of Clinical Outcome

Clinical outcomes will be assessed at the TOC Visit (Day 12) according to the following definitions:

- Clinical cure – resolution of the VVC signs and symptoms that were present at baseline without further antifungal treatment. Specifically, any sign or symptom with a score of 1 or 2 at entry should be absent (score = 0) by the TOC Visit. Any sign or symptom with a score of 3 (severe) at entry should have a score of 0 or 1 by the TOC Visit. If a new sign or symptom is observed at the TOC Visit that was not present at entry, the Investigator should state whether the new sign or symptom is related to VVC or not (ie, if related, the subject would be considered a failure; if not related, the subject may be considered a cure);
- Clinical failure – incomplete resolution of signs and symptoms of VVC that were present at baseline or new signs and symptoms have developed and require the initiation of non-study antifungal drugs; and
- Clinical indeterminate – insufficient data are available to determine if the subject is a cure or failure.

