Assessment of Mycological Outcome

Mycological outcomes will be assessed at Day 12 (± 2 days) (TOC Visit) according to the following definitions:

- Mycological eradication – a vaginal swab culture negative for growth of baseline *Candida* species;
- Mycological persistence – a vaginal swab culture positive for growth of baseline *Candida* species; and
- Mycological indeterminate – no vaginal swab culture is available, or the culture cannot be interpreted for any reason, or the culture is considered contaminated.

Assessment of Overall Response

Overall response will be assessed at Day 12 (± 2 days) (TOC Visit) according to the following definitions:

- Overall success – achievement of both a clinical cure AND microbiologic eradication;
- Overall failure – clinical failure OR microbiological persistence; and
- Overall indeterminate – insufficient data are available to determine if the subject is an overall success or failure.

The assessment of overall response at the TOC Visit is summarized below.

Summary of Overall Response at the Test-of-Cure Visit

Clinical Outcome	Mycological Outcome		
	Eradication	Persistence	Indeterminate
Cure	Success	Failure	Indeterminate
Failure	Failure	Failure	Failure
Indeterminate	Indeterminate	Failure	Indeterminate

SAFETY VARIABLES:

Safety assessments will include clinical laboratory assessments (including serum chemistry, hematology, and urinalysis), vital signs, body weight, ECGs, both complete and symptom-based physical examinations, prior and concomitant medication reporting, and adverse event reporting.

Hepatotoxicity

Hepatotoxicity will be defined as post-baseline aminotransferase $\geq 3 \times$ ULN.

Nephrotoxicity

Nephrotoxicity will be defined as a 50% increase in serum creatinine from baseline or an increase by ≥ 0.3 mg/dL.

Hypokalemia

Hypokalemia will be defined as serum potassium ≤ 2.5 mmol/L.

PHARMACOKINETIC PARAMETERS:

The PK parameters will include the following:

- AUC: area under the concentration-time curve,
- CL: clearance,
- C_{\max} : maximum plasma concentration,
- C_{trough} : concentration of pre-dose CAMB,
- $t_{1/2}$: terminal elimination half-life, and
- T_{\max} : time to maximum plasma concentration.

STATISTICAL ANALYSES:

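### The restriction on intravaginal products stops about 7 days before the Day 12 swab and scoring, and the plan does not make clear whether it ends on the same day in every arm

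*Combined protocol and SAP*

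**What the plan says.** All references are to the Synopsis of the combined protocol and SAP.

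- **Restriction.** Inclusion Criteria, item 8: "Willing to refrain from the use of intravaginal products during the treatment period (eg, douches, spermicides, condoms, tampons, and diaphragms"). No later end is given.
- **Treatment period.** The Visit Schedule describes "a 5-day treatment period (5 days with 200 mg or 400 mg CAMB or 1 day with fluconazole").
- **Dosing days.** Under Dosage Forms and Route of Administration, CAMB is given as "amphotericin B on Days 1 through 5", and for the comparator, "Fluconazole will be administered once as a single 150 mg tablet on Day 1".
- **Efficacy visit.** The Visit Schedule lists "a TOC/Early Withdrawal Visit on Day 12 (± 2 days") as a separate element.
- **Endpoints.** Efficacy Variables names three proportions, all at TOC: clinical cure, mycological eradication ("The proportion of subjects with mycological eradication at the TOC Visit (Day 12")) and overall success. Eradication is "a vaginal swab culture negative for growth of baseline" *Candida* species. Clinical cure is built from the sign and symptom scores. Overall success needs both.
- **Examinations after baseline.** "On Days 5 and 12, subjects will undergo a speculum examination of the vagina", with culture and scoring at both visits.

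**The concern.** The plan treats these products as worth keeping away from the vagina. Both study drugs are oral, so the restriction is not needed to hold a vaginal dose in place. Its evident purpose is to keep the vaginal assessments interpretable, in line with exclusion criteria 8 and 9, which remove conditions that would confuse the reading of clinical response. Yet the restriction lapses before the visit that supplies every efficacy endpoint.

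Two routes to misclassification are plausible. A douche or spermicide shortly before the swab might suppress growth and look like eradication. Irritation from a product might keep a score up and look like failure. These act in opposite directions, so even the sign of a net effect is unknown. Both are assumptions, because the documents give no data on how often such products are used or what they do to culture or scores.

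There is also a question of definition. Sites need to know on which day the restriction ends for a woman given fluconazole, and the schedule can be read two ways.

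**Working it through.** **Inputs.** Restriction ends with the treatment period (Inclusion Criteria, item 8). Treatment period: 5 days, with a bracket giving 5 days for CAMB or 1 day for fluconazole (Visit Schedule). TOC: Day 12 ± 2, so Day 10 to Day 14 (Visit Schedule). Planned mITT size 75, evaluable share 75%, about 100 randomized (Sample Size Determination). Allocation 1:1:1 to three arms (Study Design and Duration).

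**Step 1: the plan's own figure.** 75 / 0.75 = 100, which matches the stated number randomized. It does not enter the timing check.

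**Step 2: weight of one subject.** 75 / 3 = 25 mITT subjects per arm, if evaluable subjects spread evenly. 1 / 25 = 4 percentage points. This is the weight of any single misclassification, whatever its cause; it is not an estimate of bias.

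**Step 3: gap from the last restricted day to TOC.** Gap = TOC day − last restricted day, in elapsed days (full days strictly in between are one fewer).

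| Reading of the treatment period | Arm | TOC Day 10 | TOC Day 12 | TOC Day 14 |
|---|---|---|---|---|
| A: one 5-day period for all | all three | 10 − 5 = 5 | 12 − 5 = 7 | 14 − 5 = 9 |
| B: dosing days in each arm | CAMB | 5 | 7 | 9 |
| B: dosing days in each arm | fluconazole | 10 − 1 = 9 | 12 − 1 = 11 | 14 − 1 = 13 |

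Under A the arms do not differ. Under B the fluconazole gap is 11 − 7 = 4 days longer, and fluconazole subjects would also be unrestricted before the Day 5 examination and culture.

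**Step 4: does another provision close the gap?**

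- *Antifungal use.* The clinical cure definition requires that no further antifungal was used, and the Per-Protocol criteria deal with active systemic or topical antifungals before TOC. Neither reaches douches, spermicides, condoms, tampons or diaphragms as such.
- *New signs or symptoms.* Under Assessment of Clinical Outcome, the investigator states whether a new finding at TOC is related to VVC; if it is not, cure remains possible. This covers new irritation caused by a product.
- *Signs present at entry.* An item scored 1 or 2 at entry must be 0 at TOC, and an item scored 3 must be 0 or 1. No attribution step applies. A product that keeps such an item above its threshold prevents cure.
- *Culture.* The mycological definitions contain no rule about recent product use.
- *Protocol deviations.* Use after the treatment period does not breach item 8, so nothing stated would remove the subject from the Per-Protocol Population.
- *Data capture.* Concomitant medications are reported, but no question on product use is described, and tampons, condoms or douches would not obviously be recorded as medication.

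The remaining exposure is therefore the culture and the items already present at entry, for non-antifungal products.

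**Step 5: after the change.** With the restriction running to completion of TOC, the gap is 0 in every arm under either reading. The number randomized is unaffected.

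**The case against.** A reader might infer that the comparator is left open for longer than the CAMB arms, so that the distortion differs by arm. The documents do not establish this. The Visit Schedule names a single 5-day period, and its bracket reads naturally as dosing days within it. Item 8 is also a commitment made before randomization, when the woman does not yet know her arm, so a common duration is the sensible reading. On that reading the imbalance is zero. What remains is an ambiguity that sites could resolve differently.

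A reader might also infer that any product irritation at TOC counts as clinical failure. That goes too far, because the attribution step for new findings already deals with part of it. Nor is the restriction idle as written: on the common reading it runs up to the Day 5 examination and culture.

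Further points on the other side are fair. The primary objective is safety. Efficacy is secondary and summarized descriptively in a proof-of-concept trial with no formal sample size calculation, so no test or power is affected. Barrier products are not among the contraceptive methods accepted under inclusion criterion 7, which removes one reason to use them. The mechanism is assumed, not documented. A longer restriction that includes tampons is more likely to overlap menses and could affect recruitment or compliance.

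These points limit the weight of the concern and give the fix a real cost. They do not close the gap before TOC for non-antifungal products.

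**Conclusion.** The concern holds in a limited form. On the reading most favourable to the plan, the restriction ends about 7 days (5 to 9) before the swab and scoring behind all three efficacy endpoints, in every arm. Non-antifungal products that affect the culture, or keep an item present at entry above its cure threshold, are neither restricted nor asked about in that interval.

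Whether the restriction is shorter for fluconazole is unresolved. The 11-day gap (9 to 13) and the 4-day difference arise only if the treatment period is taken to mean dosing days in each arm, and should not be cited as an established imbalance.

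The size and direction of any bias cannot be computed, because frequency of use and effect are not given. What can be said is that each misclassified subject shifts an arm's rate by 4 percentage points, assuming about 25 mITT subjects per arm. This is an inexpensive improvement to how secondary, descriptive rates can be read; it does not threaten the safety objective. The conclusion rests on the Synopsis text. If a fuller section already sets a later, common end, the Synopsis should be brought into line with it.

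**What to change.** 1. Reword inclusion criterion 8 so that the restriction runs from Day 1 to completion of the TOC Visit, with the same rule in all three arms. This removes both the gap and the ambiguity about the fluconazole arm.
2. At the Day 5 and TOC visits, ask about use of intravaginal products since the last visit, recording the type of product and the date of last use.
3. Add one table repeating the three efficacy proportions without subjects who report use before the TOC swab. Label it a sensitivity analysis: use occurs after randomization and may itself depend on persisting symptoms, so the exclusion can introduce bias of its own. The mITT and Per-Protocol tables stay as planned.

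Cost: a short amendment, one case report form question asked at two visits, and one table. For subjects, it is about one more week of restriction (5 to 9 days beyond Day 5). The main downside is that the longer restriction includes tampons and may overlap menses. If that is judged too burdensome for tampons, steps 2 and 3 still apply and let the reader see whether use was common enough to matter. The contraception rule in inclusion criterion 7 is unaffected.

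### The look-back for prior antifungals depends on indication: 30 days for VVC treatment, but current use only for any other antifungal, so a woman who has just finished a systemic course is eligible

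*Combined protocol and SAP*

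**What the plan says.** Two items of the Exclusion Criteria in the synopsis deal with earlier antifungal use.

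- Item 2 applies when a woman "Is currently receiving antifungal therapy unrelated to VVC" or "has evidence of systemic fungal infections requiring antifungal therapy". Neither limb has a look-back period.
- Item 3 applies when she "Has received treatment for VVC within the past 30 days". The same item also excludes frequent recurrence.

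The only other look-back on drugs is item 17: "Has been exposed to any investigational agent during the last month (30 days or 5 half-lives, whichever is longer) prior to screening". Item 18 is a general clause for the investigator: "Has any other condition the Investigator believes would interfere with" consent or compliance, or that puts the woman at undue risk.

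Under Analysis Populations, mITT takes in "all randomized subjects who have a" *Candida* isolate from the baseline vaginal culture at the central laboratory. The Safety Population is "all ITT subjects who received at least 1 dose of study drug". Neither definition refers to prior antifungals. The Per-Protocol Population does have an antifungal rule: "Has not received another systemic or topical antifungal drug that has documented activity against the causative organism before the TOC assessment", with an exception for women already classed as failures. It gives an end point but no starting point.

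**The concern.** Whether an earlier antifungal still matters at Day 1 depends on which drug it was and when the last dose was taken, not on why it was prescribed. The two exclusions make the reason decisive. A woman who took a systemic azole for VVC 29 days ago is excluded. A woman who finished the same drug yesterday for a skin, nail or oral infection is not.

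The efficacy results at stake are clinical cure, mycological eradication and overall success at Day 12, each reported as a percentage per arm. Residual drug early in the treatment period, or a strain that survived the earlier course, could change a woman's culture or symptom outcome. That outcome would be counted under the drug she was assigned. With about 25 mITT women per arm, single outcomes are visible in these percentages.

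**Working it through.** **1. Does any other rule catch her?** Take a woman who completed a systemic antifungal for a non-VVC infection the day before randomisation.

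| Rule (synopsis) | Does it apply? |
|---|---|
| Exclusion 2, first limb | No. She is no longer receiving the drug. |
| Exclusion 2, second limb | No. The infection no longer requires therapy. |
| Exclusion 3 | No. The drug was not given for VVC. |
| Exclusions 8 and 9 | No. They concern confounding conditions, not drugs. |
| Exclusion 12 | Only if azole resistance is already known. |
| Exclusion 17 | No. It covers investigational agents only. |
| Exclusion 18 | Discretionary, and does not name confounding by earlier treatment. |
| mITT | Keeps her if the central baseline culture is positive. |
| Per-Protocol | Unclear. No start is given for the antifungal rule, and she has violated no entry criterion. |

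The written criteria admit her.

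**2. The plan's own figure.** Sample Size Determination plans 75 mITT women and assumes 75% of randomised women are evaluable: 75 / 0.75 = 100 randomised, as stated. With equal allocation to three arms, 75 / 3 = 25 mITT women per arm.

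**3. How many women?** The documents give no frequency of recent non-VVC antifungal use. Assume a fraction q of 1% to 4%, the same in mITT as among all women randomised.

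- Expected number in mITT = 75 × q: 75 × 0.01 = 0.75, and 75 × 0.04 = 3.
- Per arm, dividing by 3: 0.25 to 1.
- Chance of at least one in mITT = 1 − (1 − q)^75: 53% at q = 1%, 78% at 2%, 95% at 4%.

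**4. How large a shift?** Let f be the fraction of exposed women whose outcome changes, all in the same direction. The expected shift in an arm's rate is (exposed women per arm × f) / 25.

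- f = 1 (upper bound): 0.25 / 25 = 1 point, and 1 / 25 = 4 points.
- f = 0.25 (illustration): 0.25 to 1 point.

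**5. Is residual drug plausible?** With first-order elimination, the fraction left after t hours is 0.5^(t / half-life). The documents give no half-life for an earlier antifungal, so a range of 6 to 48 hours is assumed.

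| Time since last dose | Fraction left, half-life 6 to 48 h |
|---|---|
| 24 hours | 6% to 71% |
| 12 days (288 hours) | at most 1.6% |
| 30 days (720 hours) | below 0.01% |

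On this range, a course finished the day before can leave drug present at the start of treatment but little by the Day 12 visit. Any effect on the Day 12 outcome would come from overlap early in the study or from the strain left behind.

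**The case against.** **Exclusion 3 may not be a washout.** Its 30-day clause sits in the same item as the recurrence clause, so it can be read as describing the intended VVC population. That reading is fair and removes any formal contradiction. It does not close the gap, because there would then be no washout for completed antifungals at all.

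**Filters and records already exist.** Entry requires yeast on microscopy and at least two moderate signs or symptoms, and mITT requires a positive baseline culture. A woman whose infection has been suppressed by an earlier drug tends to drop out at these steps. Susceptibility is tested on all positive cultures, and prior medications are recorded. These points stand and reduce the likely size. However, no eligibility or population rule acts on the susceptibility results or the medication record.

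**The Per-Protocol rule may remove her.** Read literally it could reach back before Day 1, but it does not say so, and it leaves mITT untouched.

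**Stronger readings that a reader might infer:**

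- *The comparison between arms is biased.* Exposure precedes 1:1:1 randomisation and so balances on average. What remains is chance imbalance in small arms. Because the comparator is an azole, a selected strain might behave differently by arm, but the documents contain nothing that shows or sizes this.
- *Each exposed woman moves an arm by 4 points.* One changed outcome in 25 is 4 points for any woman, exposed or not. It is not evidence of carry-over, and on the assumed frequency an arm has at most about one exposed woman on average.
- *Carry-over contaminates the primary safety summaries, for example aminotransferases.* No figure in the documents links an earlier antifungal to a safety outcome, and screening chemistry would show an existing elevation. The safety claim is not made here.

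**Conclusion.** The inconsistency is real on the wording of exclusions 2 and 3, and nothing else in the available text, which is a synopsis, resolves it. The consequence is possible carry-over, not demonstrated carry-over: noise in, or a modest shift of, the descriptive Day 12 rates within arms. The figure of at most 1 to 4 points rests on an assumed 1% to 4% exposure and on every exposed outcome changing in one direction, so the realistic value is lower. No hypothesis test or margin is affected, because the efficacy analysis is descriptive. The point merits correction because the written rule itself admits these women and the change is cheap. It does not threaten the validity of the study.

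**What to change.** Reconcile exclusions 2 and 3 so that one look-back covers any systemic, vaginal or vulvar antifungal whatever the indication. Keep the exclusion for current therapy. The plan's own 30-day window is the natural candidate; the sponsor should confirm its length. In the Per-Protocol definition, state that the rule on other antifungals starts at the same point as this look-back.

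The cost is one amended eligibility line and one added phrase in the population definition. Prior medications are already collected, so sites need no new data. The downside is that a few women become ineligible or must wait. If enrolment is too far advanced to amend, the medication record allows exposed mITT women to be listed and the Day 12 rates to be shown with and without them.
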